## Study Summary

Title	Pulsed ElectroMagnetic Field (PEMF) therapy in Treating Post-Traumatic Stress Disorder (PTSD) & Trauma
Methodology	Single arm observing treatment intervention; no control, no placebo/sham
Study Duration	Estimated duration for the main protocol (the start and end of the treatment programme) is approximately 3 weeks
Study Centre(s)	Private clinic in Bristol, U.K.
Objectives	
Primary Objective: To evaluate the efficacy of Artificial Intelligence (AI) guided software rendering PEMF treatment to treat PTSD & Trauma
 
Secondary Objective: To evaluate the feasibility of AI implementation in drastically reducing the time required to train PEMF therapists, thereby allowing faster adoption of PEMF therapy into mainstream practice through use by other licensed/regulated/trained healthcare professionals such as talking therapists, nurses, doctors, social workers, and carers

Number of Actual Participants	5
Diagnosis and Main Inclusion Criteria	
Inclusion Criteria:
 
 
• Aged 18 or over
 
• Have been diagnosed with PTSD or Trauma
 
• Have been experiencing on-going, continuous symptoms of PTSD or Trauma for at least the past 6 months
 
• Can attend 6 sessions lasting 90 minutes over 3 weeks
 
• Consent and Compliance with all requirements of clinical trial, including dissemination of results, with anonymity of identity provided
 
 
Exclusion Criteria:
 
 
• Under the age of 18 years old
 
• Have not been diagnosed with PTSD or Trauma
 
• Have serious health conditions such as cancer
 
• Unable to attend 6 sessions
 

Study Product, Dose, Route, Regimen	Treatment group will receive 6 sessions, each lasting 1.5 hours of PEMF treatment over the course of 3 weeks through the CE-marked CIO devices

	classified by the U.S. Food & Drug Administration as a Type 11a Medical Device. SCIO devices contain a frequency generator and scanning technology, along with electrode harnesses that connect to the forehead, wrists, and ankles. The devices are controlled by software that is guided by A.I.
Statistical Methodology	Primary Endpoint: Symptoms of PTSD & Trauma are evaluated through a questionnaire, with scale ratings for different symptoms. Symptoms were correlated with information available on the NHS website.

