## **Methods:**

### **Study Design:**

Single-arm study involving five (5) subjects undergoing 6 90-minute sessions of Pulsed Electromagnetic Therapy. All patients received the same treatment. Harnesses were placed on the head, wrists, and ankles of the body to conduct the electromagnetic frequencies. Patients were encouraged to rest and relax whilst the therapy was conducted, as it does not require any tasks by the patient. Patients were required to complete a questionnaire before and after the trial. This questionnaire enquired about the different symptoms related to PTSD and Trauma, and asked patients to rate their symptoms on a scale. These questionnaires would form the foundation of the study's findings, as it would give a clear comparison of symptoms before and after the trial.

All aspects of the trial were exempt from a U.K. ethics committee board review because the trial was a non-invasive method of treatment, did not collect and tissue or fluid samples and the device is CE-marked and had been used in other trials previously approved and published on Clinical Trials.gov. Documents were provided on clinicaltrials.gov as evidence of this exemption.

All patients were from the inclusion criteria, and any patients exhibiting cases from our exclusion list were rejected from the pilot study. Patients were recruited through the National Centre for Electromagnetic Therapy social media pages, including Facebook, Instagram, and [www.ncet.co.uk](http://www.ncet.co.uk).

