Rate The Severity of Anger or Irritable Outbursts	Average Score: 4.8
Rate How Difficult It Is To Complete Daily Tasks	Average Score: 5.8
Rate The Severity of Your Anxiety	Average Score: 6.2

Rate Your Level of Overall Happiness	Average Score: 6.2
Rate Your Level of Satisfaction and Fulfilment In Life	Average Score: 5.8

As illustrated in the above table, symptoms varied among the patients. As an overall judgement, all patients were experiencing mild to severe symptoms related to PTSD and Trauma.

It is important to note that three of the patients had received medication for their symptoms prior to the study, but none were currently receiving treatment during the clinical trial. There was an overwhelming consensus that prescription medication from the NHS was not beneficial in helping their symptoms. One patient felt 'failed' by the therapy they had received, whilst others noted that the medication exacerbated symptoms.

Regarding sleeping, the patients were given an option to describe their sleeping situations. All patients reported a problem with sleeping. These causes ranged from harmful internal dialogue and flashbacks to insomnia and difficulty gaining a restful sleep.

These initial results will be used in the 'After Trial Results' section, where the averages will be compared, and conclusion can be drawn. Further observations will be available below the initial results to accord for any individual cases requiring attention, or further clarification on certain results.

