### 1.16

#### RATE HOW DIFFICULT IT IS TO COMPLETE DAY-TO-DAY TASKS

[figure not shown]
5 responses

1.17

RATE THE SEVERITY OF YOUR ANXIETY

[figure not shown]
5 responses

1.18

RATE THE EFFICACY OF MEDICATION YOU HAVE RECEIVED FOR YOUR CONDITION, IF ANY

3 responses

[figure not shown]

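### The statement that NHS medication did not help rests on at most three patients from a sample tilted towards non-responders, and it cannot support a conclusion about medication

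*Combined protocol and SAP*

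**What the plan says.** The Methods, Study Design section describes a "Single-arm study involving five (5) subjects undergoing 6 90-minute sessions of Pulsed Electromagnetic Therapy". The Study Summary states that there was no control and no sham.

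Under Results & Findings, Prior to the Trial, the report says that "three of the patients had received medication for their symptoms prior to the study, but none were currently receiving treatment during the clinical trial". The next sentence reads: "There was an overwhelming consensus that prescription medication from the NHS was not beneficial in helping their symptoms". The report adds that one patient felt let down by the therapy received and that others said medication had made symptoms worse. It does not say how many.

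The baseline survey contained a direct question on this point, Illustrations item 1.18: "RATE THE EFFICACY OF MEDICATION YOU HAVE RECEIVED FOR YOUR CONDITION, IF ANY". It shows three responses.

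Two features decide who could be in the sample. The Study Summary requires patients to "Have been experiencing on-going, continuous symptoms of PTSD or Trauma for at least the past 6 months". Study Design says: "Patients were recruited through the National Centre for Electromagnetic Therapy social media pages", and also names the provider's website.

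The closing conclusion, after Reflections and Considerations, describes PEMF as a beneficial, non-invasive alternative to medication for this condition.

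**The concern.** The sentence is placed among the results and reads as a trial finding about NHS medication. It has two weaknesses.

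- **Number of raters.** At most three people could speak from experience, and the report does not say how many of them held the view or how they scored it.
- **Selection.** Someone whose medication had brought lasting remission would not have continuous symptoms over the past six months, and so could not enter. Patients found through a PEMF provider's own channels may also lean towards those dissatisfied with standard care. That second step is a reasonable inference; the documents do not establish it.

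The stake lies in the closing conclusion. With no medication arm, the recalled opinions of these patients are the only data on medication in the text available for this review. If those opinions cannot carry weight, the comparison with medication has no support from the study.

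**Working it through.** The documents give no sample size, power or alpha calculation to reproduce. The check covers the denominator, the precision it allows, and the direction of the selection.

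**1. Denominator.** Prior to the Trial gives three of five patients with past medication. Item 1.18 has three responses. The two agree, so n = 3 at most.

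**2. Is a score reported?** The baseline table gives an average for 11 rating items (1.9 to 1.17, 1.19 and 1.20). Item 1.18 is the one baseline rating item without an average. The stated scale runs from 1 (very severe symptom) to 10 (symptom absent), so it does not say which end of an efficacy rating is favourable.

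**3. Precision in the most favourable case.** Assume all three reported no benefit. The exact (Clopper-Pearson) two-sided 95% lower limit for 3 out of 3 solves p³ = 0.025:

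- p = 0.025^(1/3) = 0.292, so the interval is 29% to 100%.
- The compatible share who did benefit runs up to 1 − 0.292 = 0.708, about 71%.

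This treats the three as a random sample, which they are not, so it makes no allowance for selection.

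**4. Effect of selection.** Let b be the share of medicated patients who benefit, and f the chance that a patient who benefited enters the study, relative to one who did not. Neither figure is in the documents; both are assumed over a range. Assume also that patients report accurately and independently. Among entrants, the no-benefit share is

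q = (1 − b) / [(1 − b) + b·f], and P(all three report no benefit) = q³.

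Example with b = 0.5 and f = 0.25: q = 0.5 / (0.5 + 0.125) = 0.80, and 0.80³ = 0.512.

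| b | f = 0 | f = 0.10 | f = 0.25 | f = 0.50 | f = 1 (no selection) |
|---|---|---|---|---|---|
| 0.3 | 1.000 | 0.882 | 0.737 | 0.559 | 0.343 |
| 0.5 | 1.000 | 0.751 | 0.512 | 0.296 | 0.125 |
| 0.7 | 1.000 | 0.533 | 0.252 | 0.098 | 0.027 |

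Any under-entry of patients who benefited (f below 1) makes unanimity more likely. Unanimity is certain only at f = 0.

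**5. Do the entry rules imply f = 0?** No. The inclusion criteria concern age, diagnosis, persistent symptoms, attendance and consent. The exclusions are age, lack of diagnosis, inability to attend, and "Have serious health conditions such as cancer". None mentions medication or response to it. Being off treatment is reported as an observation and is not an entry rule. The rules therefore place f below 1 but do not fix its value.

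**The case against.** A reader might infer something stronger: that the entry rules shut out everyone whose medication worked, so that eligibility alone produced the negative opinion. The documents do not support that.

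- A patient helped partly, helped for a time, or helped and then relapsed after stopping could enter.
- The report says that "all patients were experiencing mild to severe symptoms related to PTSD and Trauma", so mild cases were admitted. Two of five patients reported dreams, flashbacks or stress only at the lowest frequency offered.
- Item 1.18 asks about medication received in the past, so an earlier benefit could be recorded.
- A persistent-symptom rule does not by itself generate reports that medication made symptoms worse.

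A reader might also infer that the statement has nothing behind it but a verbal summary. That cannot be asserted either, because item 1.18 has a chart whose content is not shown. What can be said is that no figure appears in the text or the table. There may be an ordinary reason for the omission: the table exists for before-and-after comparison, and item 1.18 is not repeated in the after-trial survey (2.1 to 2.11).

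In the report's defence, the count of three stands in the sentence just before, the remark can be read as background on these patients, and the closing section says the results are not representative of the whole U.K. These points soften the baseline sentence. They do not help the closing conclusion, which makes a comparison with medication that the study had no means to make.

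**Conclusion.** The concern holds as one of bias and very small numbers. The opinion comes from at most three of five patients, with no count or score in the text or table. If all three reported no benefit, the data would still be compatible with a true benefit share of up to about 71%, before any allowance for selection. The continuous-symptom criterion under-represents people helped by medication, and the recruitment route may do so too. With an assumed benefit share of one half, the chance of three negative reports rises from 0.125 without selection to 0.512 if patients who benefited are a quarter as likely to enter. This is a tilt in a known direction and of unknown size.

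The result rests on three assumptions: that all three ratings were negative, that patients recall benefit accurately, and that the values of b and f lie in the range shown. The conclusion that the sentence is not usable evidence on medication does not depend on the particular values. The symptom change scores are unaffected.

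**What to change.** 1. In Prior to the Trial, replace the sentence with the fact: *Three of five patients had taken medication; their ratings on item 1.18 (n = 3) were ...*, giving the three values and stating which end of the scale means effective.
2. Add one sentence there: the six-month continuous-symptom criterion and the recruitment route under-represent people helped by medication, so no conclusion on its benefit is drawn. The word should be under-represent, because the criteria do not exclude such people as a class.
3. In the closing conclusion, remove the statement that PEMF is a beneficial alternative to medication, because the study had no control and no medication comparator.

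The ratings are already collected, so the cost is a few lines of text. The sponsor loses a favourable background statement and one sentence of the conclusion.

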### **During The Trial**

There were no changes to the initial plan for the clinical trial. All patients attended their arranged appointments and reported no negative side effects to the treatment.

The Lead Practitioner noted valuable verbal feedback during sessions with each patient.

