**Duration of the Study:**

The study is estimated to take place over 3 weeks, with enrolment remaining open until the trial starts. A questionnaire is required to be answered before the first session and after the final session of the clinical trial.

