### **Clinical Trial Outline**

**Prior to Trial** – Selected patients are required to fill out questionnaire provided to them by NCET.

**Week 1** – All patients receive two hours' worth of PEMF treatment across two separate sessions.

**Week 2** – All patients receive two hours' worth of PEMF treatment across two separate sessions.

**Week 3** – All patients receive two hours' worth of PEMF treatment across two separate sessions.

**Week 4** – All patients are required to fill out questionnaire provided to them by NCET. Dissemination of study and findings published.

Whilst the clinical trial is short in length, the ability for patients to get in contact with NCET is always available. Contact can be maintained between the patient and company regarding their lives after the trial. Information provided by patients after the trial has finished will be considered in the trials' findings.

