## Results & Findings

### **Prior to the Trial**

Once participants had been screened and approved for clinical trial study, they were required to fill out a questionnaire that sought to establish the specific issues that they were experiencing due to PTSD and Trauma. These responses were weighted as an average and are provided below.

For clarification, a rating of one (1) on the scale indicates a very severe case of a specific symptom, five (5) means a frequent feeling of a symptom, and ten (10) indicates that the symptom is not experienced at all. A weighted average score has been chosen as a foundation for our results, to compare them more accurately before and after the trial. However, specific notes and observations shall be included where needed.

Statements were also used, whereupon a patient would respond with either Daily (3 or more times a week), Weekly (2 to 3 times a week), Monthly (3 to 4 times a month), or Rarely (Once every 3 months or longer).

Question	Average Score
Have you experienced or witnessed a life-changing event that caused intense fear, hopelessness or horror?	All patients recorded 'Yes'.
Have you experienced either repeating dreams, flashbacks, or intense physical/emotional stress that relate back to the	Daily – 1 Patient Monthly – 2 Patients Rarely – 2 Patients

traumatic event(s)?	
Do you avoid thoughts, feelings, actions, conversations, or people related to the event?	Daily – 1 Patient Weekly – 2 Patients Monthly – 1 Patient Rarely – 1 Patient
Have you felt detached or negative towards yourself or others since the traumatic event(s) happened?	Daily – 4 Patients Monthly – 1 Patient
Do you have problems sleeping?	Daily – 1 Patient Weekly – 2 Patients Rarely – 2 Patients
Do you become increasingly irritable, angry, or engage in self-destructive behaviour?	Daily – 1 Patient Monthly – 3 Patients Rarely – 1 Patient
How long have your symptoms persisted?	Longer Than Three Years – 3 Patients Longer Than A Year – 1 Patient 8-12 Months – 1 Patient
Do you experience heightened version of anxiety, sensitivity, or depression?	Daily – 3 Patients Weekly – 1 Patient Monthly – 1 Patient
Rate Your Quality of Life	Average Score: 6
Rate The Severity of Depression	Average Score: 6.4
Rate How Difficult It Is To Fall Asleep	Average Score: 5.6
Rate The Severity of Flashbacks Relating to a Traumatic Event	Average Score: 5
Rate The Severity of Headaches or 'Brain Fog'	Average Score: 4.6
Rate The Severity of Fatigue	Average Score: 5

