## **Reflections and Considerations**

The clinical trial highlights the many benefits of PEMF therapy in treating symptoms related to PTSD and Trauma. All patients felt a significant improvement in their lives and indicated a wish to continue with PEMF therapy after the clinical trial had concluded. It can also be suggested that taking the time out of a daily schedule to attend PEMF therapy allows a patient to relax and rest. This form of meditation can be hypothesised as a beneficial side effect to PEMF therapy.

It should also be noted that patients with previous experience with Cognitive Behavioural Therapy (CBT) were more receptive to treatment, especially within the first two sessions. This is due to the selected patients (two of the five patients in the study) being able to communicate their triggers and emotions more clearly to the Lead Practitioner during PEMF treatment. This allowed the patients to experience a form of CBT with the clinical trial staff, whilst providing them time to relax out of their regular schedule. These two patients especially saw an improvement with sleeping, indicating that the opportunity to vocalise their symptoms and emotions helped them alleviate PTSD-related problems.

Whilst the clinical trial was a success in achieving the primary objective, there are numerous considerations and reflections for further clinical trials into PEMF therapy.

- A larger study would be beneficial in further analysing the benefits of PEMF therapy in treating PTSD and Trauma. Access to a larger cohort of volunteers, with a larger time frame of more PEMF sessions would produce a larger result pool. This would also allow for a control group, a treatment group, and a sham group to compare results more accurately and draw wider conclusions to the specific benefits of PEMF treatment.
- Twice weekly sessions proved to be tiring for patients (see Patient Three's statement above), therefore a longer, more spaced-out study would allow patients to recover from PEMF treatment before their subsequent sessions. This would remove the risk of exhausting the patients which may hamper accurate results of the study.
- This study was restricted due to financial and time restraints. Staff numbers were restricted to the Lead Practitioner and a Research Assistant to disseminate results. The financial impact of conducting a clinical trial for free dictated that the trial would be short to make it viable for the sponsor's funding.

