It is of the opinion of the National Centre of Electromagnetic Therapies that this clinical trial was a success in meeting its primary objective in improvement symptoms related to PTSD and Trauma through PEMF. The clinical trial has highlighted the many benefits of PEMF treatment. Nearly all studied symptoms improved for all patients during the trial, and there was no worsening of symptoms recorded. The evidence provided within this document attests to these conclusions.

Therefore, it is recommended that further clinical trials into the development of Pulsed Electromagnetic Therapy as treatment for symptoms of PTSD and Trauma should be conducted. It is our goal to conduct a similar study on a far larger scale, with more participants and a longer trial period. This conclusion has been reached due to the promising positive benefits of PEMF therapy shown through this clinical trial. The clinical trial also concludes that PEMF therapy is a beneficial, non-invasive alternative to prescription medication in relation to PTSD and Trauma. Whilst the results cannot claim to be representative of the entire U.K., the clinical trial has indicated that there are significant benefits to Bio-Resonance treatment and should therefore be studied further.

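### The results section reports no negative side effects without qualification, while the report's reflections say the sessions tired patients; the two statements need to be reconciled

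*Combined protocol and SAP*

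**What the plan says.** The During The Trial section gives the trial's tolerability result in one sentence: "All patients attended their arranged appointments and reported no negative side effects to the treatment". It attaches no qualifier and no definition of a side effect. It then says that the practitioner noted verbal feedback from each patient.

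Reflections and Considerations lists lessons for future trials. One of them begins "Twice weekly sessions proved to be tiring for patients" and refers to one patient's statement. It goes on to say that a study with sessions further apart "would allow patients to recover from PEMF treatment before their subsequent sessions", and then: "This would remove the risk of exhausting the patients which may hamper accurate results of the study".

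Fatigue is also a questionnaire item, "Rate The Severity of Fatigue", scored from 1 (very severe) to 10 (absent). Its mean is 5 before the trial and 6.8 after it. Duration of the Study fixes when it was rated: "A questionnaire is required to be answered before the first session and after the final session of the clinical trial". The Clinical Trial Outline puts the second rating in week 4, after three weeks of sessions: "All patients are required to fill out questionnaire provided to them by NCET".

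**The concern.** The results sentence, read as written, means that none of the five patients reported any unwanted effect. The reflections describe an unwanted effect, apply it to patients in the plural, and speak of recovering from the treatment itself. A reader who takes tolerability from the results section alone would record zero side effects. A reader who reaches the reflections would not.

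This sentence is the only side-effect result in the available text. The report goes on to recommend a larger and longer trial and to present the therapy as an alternative to medication, and tolerability bears on both. What is at stake is what the report can say about tolerability; no symptom score depends on it.

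**Working it through.** The documents state no sample-size or event figure to reproduce, so the check is mainly a comparison of text.

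**1. The two statements side by side**

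| | During The Trial | Reflections and Considerations |
|---|---|---|
| Content | No negative side effects | Sessions were tiring |
| Who | All patients | Patients, plural, no count; one statement cited |
| Linked to | The treatment | Twice-weekly sessions, then recovery from PEMF treatment |
| Status | Reported result | Tiredness as observed; exhaustion as a risk that a future design would remove |

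No section in the available text cross-refers between them or excludes tiredness from side effects.

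**2. How the report uses the term.** Potential Benefits and Risks to Patients describes headaches or dizziness in about 1% of the investigator's patients, not severe and lasting no more than 12 hours, and calls this a side effect. Mildness and short duration therefore do not by themselves put a complaint outside the term as this report uses it.

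**3. Whether the fatigue item resolves the clash.**
- Change in mean: 6.8 − 5 = +1.8 points, an improvement. This agrees with the figure under After The Trial.
- Timing: 2 questionnaires, one before session 1 and one after session 6. Six sessions leave 6 − 1 = 5 gaps, and 0 of the 5 gaps contain a rating.
- Tiredness that came and went during the course could leave no trace in this before-and-after comparison. The improved mean and the tiring sessions can both be true, so the item neither supports nor contradicts the results sentence.

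**4. Size.** The results sentence implies 0 of 5 patients. The number who were tired is not in the available text, so it is treated here as an unknown x, with x from 1 to 5 as an assumed range. Exact (Clopper-Pearson) 95% intervals, for context only:

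| x of 5 | Proportion | 95% interval |
|---|---|---|
| 0 | 0% | 0% to 52.2% |
| 1 | 20% | 0.5% to 71.6% |
| 2 | 40% | 5.3% to 85.3% |
| 5 | 100% | 47.8% to 100% |

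For x = 0 the upper limit is 1 − 0.025^(1/5) = 1 − 0.478 = 0.522. With five patients, a single case moves the reported proportion from 0% to 20%.

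**The case against.** The strongest reply is that both statements can be true. The results sentence concerns effects of the treatment, whereas the reflections begin from how often patients had to attend, which may be visit burden. This reading is open and cannot be ruled out. It does not remove the problem, because the same item then speaks of recovery from PEMF treatment and the results sentence draws no such distinction. The authors need to say which they mean.

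A second reply is that the report uses the phrase loosely. Potential Benefits and Risks to Patients says that no negative side effects have been recorded and, in the next sentence, describes headaches or dizziness. That is fair, and it makes a literal zero-symptom reading of the results sentence less secure. It is also a reason to state what the sentence covers.

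A third is that the patient statements are not in the text available for review and may give number, severity, duration or a qualification. This stands as a limit. Such text could supply the count, but the results sentence would still carry no qualifier or cross-reference.

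A reader might also infer three stronger things that the documents do not support:
- **That the tiredness was concealed.** It was not; the reflections disclose it.
- **That the conclusion repeats the no-side-effects claim.** It does not. Its words are "there was no worsening of symptoms recorded", which concern symptoms and make no statement on side effects.
- **That exhaustion distorted the efficacy results.** The report names this only as a risk that a different design would remove, not as something observed.

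**Conclusion.** The point holds in a limited form. The only side-effect result in the available text is unqualified, and it clashes with the report's own account of tiring sessions; the before-and-after fatigue mean does not reconcile them. The size in patients is unknown: 0 of 5 as the results section reads, and an uncounted number according to the reflections. No efficacy figure changes.

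This rests on two assumptions: that no patient statement outside the available text already reconciles the passages, and that the reflections describe tiredness that patients in this trial actually reported, as the past tense and the cited statement indicate. It does not depend on classing tiredness as a side effect of the device. Whether it was one is the question that the report leaves open. Nothing here bears on which session schedule is right.

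**What to change.** In During The Trial, keep the attendance statement and replace the unqualified side-effect clause with three elements:

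1. *Tiredness was reported during the course by x of 5 patients (see Reflections and Considerations)*, with x taken from the existing session notes and patient statements. If these do not allow a count: *tiredness was reported but not counted*.
2. One sentence saying whether the authors regard the tiredness as a side effect of the treatment or attribute it to the visit schedule, and noting that a single-arm design cannot separate the two.
3. *Apart from this tiredness, no negative effects were reported*, if the records support it. This wording leaves the classification to the second element.

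The cost is a few sentences and, where the notes allow, one count from existing records; no new data are needed. There are two drawbacks: the safety statement becomes slightly less favourable, and a count from unstructured notes may be too low.
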